### 6.5 Sensitivity Analyses

Sensitivity analyses will be performed to test the robustness of the External Comparator analysis results for LVEF. Analyses exploring the hyperparameters of the propensity score matching algorithm will be presented. Random ordering will be employed to test the sensitivity of the match algorithm to sort order. Furthermore, results from an optimal propensity matching algorithm with appropriate k and caliper width will be presented.

The following outcome analyses will be performed using the matched set from the primary analysis:

- A Wilcoxon rank test comparing the change from baseline between the two groups,
- Change from baseline to Month 24 using an ANCOVA model with treatment as a factor and baseline and age as potential covariates.

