# 6.4 External Comparators (Exploratory Efficacy Part 1)

For both the ECP and ECC, propensity score matching will first be attempted to produce an appropriate sample of real-world controls for comparison with the treated subjects from HOPE-2 OLE. If propensity score matching is not appropriate due to small sample size or other limiting factors, then cohort matching will be employed next. In either case, baseline characteristics available in both studies (e.g. baseline LVEF/PUL, age, etc.) will be utilized in the matching algorithm. External Comparator analyses will not be performed or reported if cell sizes are not sufficiently large for statistical analyses after either cohort or propensity score matching is performed. This will be determined separately and independently for the ECP and ECC datasets. If matching is not feasible summary level data may be analyzed.

If propensity score matching is feasible, the following parameterization will be utilized. Greedy nearest-neighbor matching using the logit of the propensity score and an appropriate caliper will be utilized to select matches. Up to 5 matches per treated subject will be used, given available data. Caliper width will be selected such that no treated samples are dropped from the analysis, i.e. at least one control subject will be selected per treated subject. Treated subject records will be sorted in ascending order by propensity score probability.

Baseline characteristics of matched subjects juxtaposed with treated subjects will be reported. In the case of propensity score matching, weighted statistics will be utilized including in analysis and modeling where appropriate.

Indexed volumes will be harmonized between studies: the body-surface area calculation utilized in the HOPE-2 study will be applied to the ECC to recalculate indexed volumes.

The HOPE-2 Month 12 visit will be utilized as the HOPE-2-OLE baseline visit for cardiac MRI parameters, as no cardiac MRI measurements were conducted at the HOPE-2-OLE baseline visit.

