The treated and matched controls from the ECP/ECC will be compared using a continuous-time, random slope mixed model with age, baseline, and treatment-by-time interaction. If significant baseline imbalances persist after cohort matching, a baseline-by-treatment interaction term will be included in the model. Slope differences between groups will be presented along with the estimated treatment difference at 24 months (for ECC) and 36 months (for ECP) with corresponding 95% confidence intervals and associated two-sided p-values. The Kenward Roger approximation will be utilized to calculate denominator degrees of freedom. A percentile rank transformation will be applied to the change from baseline and baseline values in case model assumptions are violated.

Furthermore, a global statistical test (GST) may be employed to explore the totality of evidence across multiple cardiac endpoints, such as Left Ventricular Ejection Fraction, Indexed Left Ventricular End Systolic Volume, Indexed Left Ventricular End Diastolic Volume, and other cardiac MRI measures collected in HOPE-2 OLE and in the ECC. The GST will be constructed as follows:

• For each distinct parameter in the GST, calculate the standardized change from baseline as follows:

$$chg'_{i,t,p} = \frac{x_{i,t,p} - \mu_p}{\sigma^{pooled}_{t,p}}$$

where *i*, *t*, *p* represent the *i*th subject, the timepoint (visit) *t*, and the *p*th parameter in the GST, *x* represents the raw score (analysis value),  $\mu$  represents the mean baseline value for parameter,  $\sigma^{pooled}$  is the standard deviation of  $x_{t,p}$  pooled between control and treatment arms, and *chg'* is the standardized change from baseline.

Then, by subject and visit, calculate the mean standardized change from baseline as:

$$chg_{i,t}^{gst} = \frac{1}{n} \sum_{p=1}^{n} chg_{i,t,p}',$$

where  $chg^{gst}$  represents the change from baseline score of the GST.

Baseline values will be calculated in the same manner using baseline analysis values for each parameter and only with the baseline visit. If any of the baseline components do not have a calculable baseline value, baseline will be calculated from the available measures. Scales will be directionally aligned in determination of the final score.

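### SAP 6.5 leaves the LVEF Wilcoxon test unspecified; run as an ordinary pooled test on 1-to-5 matched data, it can be more biased than the adjusted analysis it checks

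*SAP*

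**What the plan says.** SAP 6.4 builds the comparator group by greedy nearest-neighbour propensity matching. The ratio is variable: "Up to 5 matches per treated subject will be used, given available data", with the caliper chosen so that "at least one control subject will be selected per treated subject". If propensity matching is unsuitable, cohort matching replaces it.

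On weighting, SAP 6.4 says: "In the case of propensity score matching, weighted statistics will be utilized including in analysis and modeling where appropriate". It does not define the weight, and it gives no weighting rule for cohort matching.

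The main comparison is a "continuous-time, random slope mixed model with age, baseline, and treatment-by-time interaction", so it adjusts for age and baseline.

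SAP 6.5 then lists checks for LVEF. It introduces the outcome checks with "The following outcome analyses will be performed using the matched set from the primary analysis" and names two. One is "A Wilcoxon rank test comparing the change from baseline between the two groups". The other is an ANCOVA, for which the SAP does name Month 24 and gives baseline and age as possible covariates. The Wilcoxon line has no such detail.

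**The concern.** A sensitivity analysis is useful if it relaxes one assumption and leaves the rest of the comparison intact. Here the rank test is presumably meant to relax the distributional assumptions of the mixed model. An ordinary rank-sum test on the pooled matched set changes two other things as well.

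- It counts every control equally. Subjects with five matches then contribute five times as many controls as subjects with one, so the pooled controls resemble the easy-to-match treated subjects rather than all of them.
- It has no covariates, so any imbalance in age or baseline LVEF that survives matching goes straight into the comparison.

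If the test disagrees with the main model, a reader cannot tell fragility from imbalance. If it agrees, the agreement may owe something to imbalance. As written, the choice of weights, sets and timepoint could also be made after the data are seen.

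**Working it through.** The documents give no power or error rate for this test, so there is no planned figure to reproduce. The mechanism was checked by arithmetic and then by simulation.

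**1. Set sizes.** Inputs: 13 treated subjects (SAP 4.1) and 1 to 5 controls each (SAP 6.4). As an illustration, let 6 treated subjects have 1 match and 7 have 5.

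- Pooled controls: 6 × 1 + 7 × 5 = 41.
- Share of controls from the 5:1 sets: 35/41 = 85%.
- Share of treated subjects in those sets: 7/13 = 54%.

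Weighting each control by 1/k, where k is the size of its set, restores 54%. If all sets were the same size, weighting would change nothing.

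**2. Simulation with no treatment effect.** From the SAP: 13 treated; greedy matching on the logit of the propensity score, treated sorted ascending; up to 5 controls; a caliper that keeps every treated subject. Assumed: pools of 40, 80 or 200 controls; matching without replacement, filled in rounds; treated subjects older and lower at baseline by the stated shift; change = −0.5 × age + 0.25 × baseline + noise (SD 1, covariates in SD units). There were 600 runs per scenario, so the Monte Carlo standard error at 5% is √(0.05 × 0.95/600) = 0.9 percentage points.

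Bias before matching is −0.5 × shift + 0.25 × (−shift) = −0.75 × shift: −0.375 at 0.5 SD and −0.60 at 0.8 SD.

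| Result (pool 40 / 80 / 200) | Shift 0.5 SD | Shift 0.8 SD |
|---|---|---|
| Bias, pooled unweighted difference | −0.34 / −0.16 / −0.09 | −0.52 / −0.31 / −0.15 |
| Bias, 1/k-weighted difference | −0.19 / −0.05 / −0.03 | −0.41 / −0.19 / −0.06 |
| Bias, ANCOVA on age and baseline | −0.02 / 0.01 / −0.01 | 0.03 / 0.00 / 0.00 |
| Rejection, pooled Wilcoxon | 13.0% / 4.7% / 3.5% | 29.0% / 14.3% / 5.5% |
| Rejection, van Elteren by matched set | 9.3% / 4.2% / 3.0% | 18.2% / 9.3% / 5.5% |
| Rejection, ANCOVA | 5.5% / 4.7% / 4.5% | 5.0% / 5.3% / 4.7% |

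The ANCOVA is a single-timepoint stand-in for the covariate adjustment of the mixed model; the mixed model itself was not simulated. The sign of the bias follows the assumed direction of the shift.

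**3. When the problem disappears.** With no shift, bias was below 0.02 for every method and the pooled Wilcoxon rejected 2.3% to 3.5%. With a 0.5 SD shift, a pool of 80 and covariates unrelated to outcome, bias was below 0.01 and rejection 6.3%.

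**4. How much is due to weighting.** Share of the pooled bias removed by 1/k weights:

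- Shift 0.8 SD, pool 40: (0.522 − 0.406)/0.522 = 22%.
- Shift 0.8 SD, pool 80: (0.314 − 0.192)/0.314 = 39%.
- Shift 0.5 SD, pool 40: (0.335 − 0.191)/0.335 = 43%.
- Shift 0.5 SD, pool 80: (0.164 − 0.046)/0.164 = 72%.

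The remainder is imbalance that only covariate adjustment addresses.

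**5. Candidate replacement.** A further null simulation (13 treated, shift 0.6 SD, pools of 40 / 80 / 150) gave bias of 0.38 / 0.21 / 0.10 SD unweighted against 0.24 / 0.10 / 0.01 SD set-weighted. Rejection was 17% / 9% / 4% for the pooled Wilcoxon, 10% / 7% / 5% for van Elteren, and 4% / 7% / 6% for a rank test on residuals from baseline and age.

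**The case against.** The strongest reply is that the SAP never says the test is unweighted. SAP 6.4 carries a general rule that "weighted statistics will be utilized including in analysis and modeling where appropriate", and the test runs on the set to which that rule applies. This stands in part. A reader might infer that the SAP prescribes an unweighted pooled test, but SAP 6.5 is silent on the matter. Still, the rule does not settle it: the weight is undefined, the clause is limited to propensity matching and to where it is appropriate, and an ordinary rank-sum test takes no weights. Applying the rule would mean choosing a different test that the SAP does not name.

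Second, the largest effects come from a pool of 40, which cannot supply five controls each (13 × 5 = 65). For small samples the SAP provides a way out: "If propensity score matching is not appropriate due to small sample size or other limiting factors, then cohort matching will be employed next". It also drops the comparison if the matched cells are too small. So that scenario may never be analysed this way. At a pool of 80, however, the pooled test still rejected 14.3% at the 0.8 SD shift, and cohort matching does nothing about the missing covariates.

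Third, other safeguards exist. SAP 6.4 reports matched baseline characteristics, and SAP 6.5 also plans ANCOVA, random match order and optimal matching. The comparison is exploratory, SAP 4.5 states no pre-specified test hypotheses, and no decision rests on this test. All of this stands and keeps the point minor.

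**Conclusion.** The Wilcoxon line is under-specified, and its most natural reading is a weak check. With unequal set sizes, a small control pool and sources that differ on covariates related to LVEF change, an ordinary pooled test can be more biased than the covariate-adjusted analysis that it is meant to support. Under the assumed scenarios, pooled bias ran from 0.09 to 0.52 SD with a shift of 0.5 or 0.8 SD, against at most 0.03 SD with adjustment. With pools of 150 or 200, rejection was 3.5% to 5.5% even under a shift, although a bias of up to 0.15 SD remained. With no imbalance there was no material effect.

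Two stronger readings should be resisted. The documents do not show that the test will be more biased than the main model in this trial: pool size, covariate differences and covariate effects are not given, so the figures are illustrations and not estimates. Nor is missing weighting the whole explanation, since much of the gap comes from the missing age and baseline adjustment. Nothing here impugns the main LVEF comparison itself. This is a low-severity improvement to an exploratory sensitivity analysis.

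**What to change.** Replace the Wilcoxon line in SAP 6.5 with a two-sided rank test at Month 24 on the residuals of LVEF change from baseline after regression on baseline LVEF and age (an aligned rank test), to be used after propensity or cohort matching. State which subjects the regression is fitted to, for instance both groups together without a treatment term.

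Where propensity-matched sets exist, a van Elteren test stratified by set may be added. It should not be the only replacement, because it still rejected up to 18.2% in the assumed scenarios. If any weighted statistic is reported, define the weight, for example 1/k for each control in a set of k.

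The cost is about one line of SAP text. It needs no new data and no change to the matching or the main model.

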# 6.6 Gap Phase (Exploratory Efficacy Endpoints Part 2)

Observed values and change from baseline will be summarized (n, mean, SD, minimum, and maximum) for PUL 2.0 Combined Total Score across the Gap Phase, which runs from Month 12 HOPE 2 (the baseline for these analyses) to Baseline/Day 1 HOPE-2-OLE.

# 7 SAFETY ANALYSES

Listings and summaries of the safety parameters will be done for the safety population. Safety parameters are described below.

### 7.1 Adverse Events

AEs will be coded using MedDRA coding system (Version 23.1).

The following AEs are defined as TEAEs:

- AEs that occur after the initiation of the IV catheter placement for the initial dose of IP
- AEs with a completely missing start date, or similarly, AEs that start the same month and year as IP administration but that have a missing start day.

TEAEs are considered to be related to IP/administration procedure if the relationship of the particular event is marked as "possible" or "probable".

Subject listings of all AEs as reported will be provided. Serious AEs and TEAEs that are assessed as related to the IP or administration procedure, and hypersensitivity reactions/acute respiratory decompensation will be listed separately.

All summary tables will be reported using TEAEs. Additionally, TEAEs by maximum severity and TEAEs that are related to the IP or administration procedure and hypersensitivity reactions/acute respiratory decompensation will be summarized.

TEAEs will be displayed by MedDRA SOC and PT, with subjects who experience the same TEAE counted only once for that event and subjects who have more than one TEAE within a SOC counted only once in that SOC. The numbers and percentages of subjects with an event, as well as the number of events that were reported, will be calculated.

The summary tables will be prepared first for 12 months from the date of first IP administration during the OLE Phase and then again through 60 months in the OLE Phase.

# 7.2 Vital Signs, Height, Weight, and BMI

Vital signs will include systolic and diastolic blood pressures, pulse rate, respiratory rate, body temperature, and blood oxygen saturation (SpO2). Observed and change-from-baseline values will be summarized at each post-baseline visit. Baseline will be defined as the pre-infusion samples that are collected on Day 1. Scheduled assessments will be summarized, and unscheduled events will only be listed.

Listings of vital signs, ulna length, height, weight, and BMI will be provided. Height will be calculated from the subject's ulna length.

# 7.3 Physical Examination

All physical examination results will be listed. A shift table will be presented by body system for physical examination findings.

### 7.4 Elevation of HLA antibodies against the donor cells (i.e., DSAs)

Mean fluorescence intensity (MFI) will be listed for donor specific antibodies. The listing will highlight MFIs >1000 with bold and italicized type.

# **8 DEVIATIONS FROM STATISTICAL METHODS IN THE PROTOCOL**

The statistical methods in this statistical analysis plan are consistent with those described in the Amendment 5 of the study protocol with the following exceptions:

- The wall thickness percentages for the cardiac MRI parameters (secondary efficacy) were not collected and thus not available for descriptive analysis.
- Cardiac MRI parameters were not collected at 12-months for the HOPE-2-OLE study.
- The secondary analyses (Distal level PUL 2.0 and Mid-level (elbow) PUL 2.0) which involved subgroup analyses based on the entry level item of PUL 2.0 at baseline will be reported without the subgroups due to the small sample size of the subgroups.

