### 6.2.2. Secondary Endpoints

The *secondary safety endpoint* is the incidence and severity of all treatment-emergent adverse events from baseline through Month 60.

The *secondary efficacy endpoints* include the changes from baseline through the Month 60 timepoint for the following:

- Upper body functionality using PUL 2.0 assessment at Months 12, 24, 36, 48, and 60
- Distal-level PUL 2.0 for subgroup of subjects with entry level scores of 2 and 3 at Months 12, 24, 36, 48, and 60
- Mid-level PUL 2.0 for subgroup of subjects with entry level scores of 4 and 5 at Months 12, 24, 36, 48, and 60
- Left Ventricular Ejection Fraction (LVEF) (i.e., Cardiac MRI) measurement at Month 24, 36, 48, and 60
- Left Ventricular End Systolic Volumes-Indexed (ESVI) measurement at Month 24, 36, 48, and 60
- Left Ventricular End Diastolic Volumes-Indexed (EDVI) measurement at Month 24, Month 36, 48, and 60
- Other cardiac parameters, including but not limited to mass, unindexed volumes, cardiac output, wall thickening percentage, and end diastolic and end systolic wall thickness at 24, 36, 48, and 60

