#### 2.2.4 Secondary Efficacy Endpoints

The *secondary efficacy endpoints* include the change from baseline (PUL 2.0: HOPE-2-OLE Baseline, Cardiac MRI: HOPE-2 Screening Baseline) through Month 60 for the following:

- Upper body functionality using the PUL 2.0 assessment (i.e. Upper level PUL:2.0) at Months 24, 36, 48, and 60
- Distal level PUL 2.0 for subgroup of subjects with entry level PUL 2.0 scores of 2 and 3, at Month 12, 24, 36, 48, and 60
  - Entry level at baseline of HOPE-2-OLE
- Mid-level PUL 2.0 for subgroup of subjects with entry level PUL 2.0 scores of 4 and 5, at Month 12, 24, 36, 48, and 60
  - Entry level at baseline of HOPE-2-OLE
- Left Ventricular Ejection Fraction (LVEF (i.e. Cardiac MRI) at Month 24, 36, 48, and 60.
- Left Ventricular End Systolic Volume, Indexed (Cardiac MRI) at Month 24, 36, 48, and 60.
- Left Ventricular End Diastolic Volume, Indexed (Cardiac MRI) at Month 24, 36, 48, and 60
- Other cardiac parameters, including but not limited to mass, unindexed volumes, and end diastolic and end systolic wall thickness at 24, 36, 48, and 60

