# 5.3 Demographics and Baseline Characteristics

Demographic and baseline characteristics will be listed and summarized for the safety population. Demographic characteristics will consist of sex, ethnicity, and race, as collected in the preceding HOPE-2 trial, and age in years at HOPE-2 OLE baseline.

Baseline characteristics will include ulna length, height, weight, body mass index (BMI), baseline PUL 2.0 entry item score, and baseline PUL 2.0 entry item score binary stratification (2, 3 vs 4, 5), where entry item score refers to the baseline OLE score, and length of Gap Phase in days.

Subject height will be calculated from the subject's ulna length: Height (cm) = [4.605 x Ulna Length (cm)] + [1.308 x Age (years)] + 28.003.

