# 6.3 Secondary Efficacy Endpoints

The *secondary efficacy endpoints* include the change from baseline (PUL 2.0: HOPE-2-OLE Baseline, Cardiac MRI: HOPE-2 Month 12) through Month 60 for the following:

- Upper body functionality using PUL 2.0 assessment (i.e. Upper level PUL:2.0) at Months 12, 24, 36, 48, and 60
- Distal level PUL 2. at Month 12, 24, 36, 48, and 60
- Mid-level (elbow) PUL 2.0 at Month 12, 24, 36, 48, and 60
- LVEF (i.e. Cardiac MRI) at Month<del>,</del> 24, 36, 48, and 60.
- Left Ventricular End Systolic Volume, Indexed (Cardiac MRI) at Month, 24, 36, 48, and 60.
- Left Ventricular End Diastolic Volume, Indexed (Cardiac MRI) at Month, at Month 24, 36, 48, and 60.
- Other cardiac parameters, including but not limited to mass, unindexed volumes, and end diastolic and end systolic wall thickness at 24, 36, 48, and 60.

Observed values and change from baseline will be summarized (n, mean, SD, minimum, and maximum) for all secondary endpoints. Descriptive statistics for the External Comparators, ECP and ECC (section 6.4) will be presented for comparison with endpoints for which data are available.

Further comparisons will be formally made for the 24- and 36-month visits (if available) utilizing real-world evidence from external sources. The data and methods utilized for these comparisons is described in the next section.

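### Two PUL 2.0 secondary endpoints are defined in entry-score subgroups, but the SAP plans to summarise them only in the full Safety Population

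*SAP*

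**What the plan says.** Protocol 6.2.2 lists two secondary endpoints that are each restricted by entry score: "Distal-level PUL 2.0 for subgroup of subjects with entry level scores of 2 and 3 at Months 12, 24, 36, 48, and 60" and "Mid-level PUL 2.0 for subgroup of subjects with entry level scores of 4 and 5 at Months 12, 24, 36, 48, and 60". The SAP's own endpoint list, section 2.2.4, keeps both restrictions: "Distal level PUL 2.0 for subgroup of subjects with entry level PUL 2.0 scores of 2 and 3" and "Mid-level PUL 2.0 for subgroup of subjects with entry level PUL 2.0 scores of 4 and 5". It adds that the entry score is the one at the HOPE-2-OLE baseline.

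SAP 6.3, which sets out the analysis, drops the restriction. The mid-level item reads "Mid-level (elbow) PUL 2.0 at Month 12, 24, 36, 48, and 60", and the distal item is likewise listed without a subgroup. For all secondary endpoints it plans n, mean, SD, minimum and maximum. The third bullet of SAP 8 declares the change from the protocol and gives the reason: both endpoints "will be reported without the subgroups due to the small sample size of the subgroups".

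Three other sections bear on the point. SAP 4.6 uses the Safety Population for all efficacy analyses, and SAP 4.1 puts the OLE phase at 13 subjects, all treated. SAP 5.3 still lists and summarises the "baseline PUL 2.0 entry item score binary stratification (2, 3 vs 4, 5") variable at baseline. SAP 6.1 lists each subject's total and change for each PUL dimension.

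**The concern.** An endpoint is defined by its population as well as by its measurement. Here the two endpoint names stay the same while the population changes from an entry-score subgroup to everyone treated. A reader who takes the definition from SAP 2.2.4 and the result from the table would attach a full-sample mean to a subgroup endpoint.

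The entry item sets the functional level at which PUL testing starts (Protocol 12.1, SAP 6.1). It is therefore plausible that change in a given dimension differs by entry score, and pooling cannot be assumed to be harmless. At stake is the meaning of two descriptive secondary endpoints. No error rate, sample size or primary result is affected.

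**Working it through.** The plan states no power, precision or sample-size figure for these endpoints, so there is nothing to reproduce. The check compares the sections and then works out what pooling does to the mean.

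**1. Sections side by side**

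| Place | Distal level | Mid level |
|---|---|---|
| Protocol 6.2.2 | entry 2 and 3 | entry 4 and 5 |
| SAP 2.2.4 | entry 2 and 3, OLE baseline | entry 4 and 5, OLE baseline |
| SAP 6.3 | no subgroup | no subgroup |
| SAP 8 | subgroup dropped, small n | subgroup dropped, small n |

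SAP 6.3 and 8 agree with each other and disagree with SAP 2.2.4. The only subgroup analysis in SAP 4.7 is baseline LVEF above 45%, for cardiac parameters. No section plans a summary of either dimension by entry score.

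**2. Pooled mean against defined mean**

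Inputs: N = 13 (SAP 4.1). The subgroup sizes and mean changes are not in the documents. I assume that every subject has an entry score of 2 to 5 and is observed at the visit. Let n_sub be the size of the defined subgroup, m_sub its mean change and m_other the mean change of the rest.

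- Pooled mean = (n_sub/13) x m_sub + (1 - n_sub/13) x m_other
- Pooled mean minus m_sub = (1 - n_sub/13) x (m_other - m_sub)

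For n_sub = 7 the factor is 6/13 = 0.46; for n_sub = 6 it is 7/13 = 0.54. With a 7/6 split one endpoint takes each value. For a 2-point difference in mean change the shifts are 0.92 and 1.08 points.

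**3. Precision of a subgroup row**

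The 95% half-width in SD units is t(0.975, n - 1)/sqrt(n). SAP 6.3 plans no interval for these endpoints, so this only indicates how imprecise the added rows would be.

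| n_sub | Shift per 1-point difference, (13 - n_sub)/13 | Half-width, SD units |
|---|---|---|
| 2 | 0.85 | 8.98 |
| 3 | 0.77 | 2.48 |
| 5 | 0.62 | 1.24 |
| 6 | 0.54 | 1.05 |
| 7 | 0.46 | 0.92 |
| 8 | 0.38 | 0.84 |
| 10 | 0.23 | 0.72 |
| 11 | 0.15 | 0.67 |
| 13 (pooled) | 0 | 0.60 |

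The smaller the defined subgroup, the further the pooled mean can lie from it, and the less precise its own summary would be.

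**4. Does the stated reason carry the change?**

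The planned output in SAP 6.3 is descriptive and can be produced for a small group. SAP 6.2 already splits the same 13 subjects by their HOPE-2 arm and reports means, SDs and 95% confidence intervals for each part. The entry-score variable needs no new derivation.

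**The case against.** The best defence is that the change is open. SAP 8 exists to record departures from the protocol, and it names both endpoints, what is dropped and why. A programmer reading SAP 6.3 with SAP 8 knows what to produce. That stands: a reader might infer a concealed change, and the documents do not support it. What SAP 8 leaves undone is aligning the SAP's own section 2.2.4.

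A reader might also infer that the subgroup results are lost. They are not. SAP 4 promises listings of all collected data for all subjects, SAP 5.3 lists the entry score, and SAP 6.1 lists change by dimension. With 13 subjects the subgroup means can be computed by hand. What is missing is a planned summary.

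Small n is also a better reason than it first appears. SAP 6 plans p-values for each outcome, and Protocol 13.1 allows tests for information. A nominal p-value in two or three subjects would be of little use, and at n = 3 the half-width is 2.48 SD. This supports withholding inference from the subgroups. It does not support withholding a descriptive row.

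Three further inferences go beyond the text:

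- Pooling dilutes a decline. The sign of m_other - m_sub is unknown, so pooling could overstate or understate the subgroup change.
- Subjects scoring outside 2 to 5 enter the pooled rows. Nothing shows that any exist, and SAP 5.3 treats the split as binary.
- Each dimension was picked because it suits its subgroup. The documents pair dimensions with entry scores but give no rationale.

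**Conclusion.** The point holds as a mismatch between definition and analysis that should be corrected. Following the plan gives all-subject summaries in place of the two endpoints defined in Protocol 6.2.2 and SAP 2.2.4, and the stated reason does not justify omitting a descriptive row.

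The algebra of the shift is certain, but its actual size and direction are not. The range is 0.23 to 0.77 points per 1-point difference for n_sub from 10 down to 3, and 0.46 to 0.54 at a 7/6 split. A very uneven split such as 11/2 would leave the larger subgroup's mean nearly unchanged, at 0.15 points. These figures assume 13 observed subjects, all with entry scores 2 to 5; n may be lower at later visits.

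The importance is moderate. These are descriptive secondary endpoints in a single-arm extension with no pre-specified hypotheses (SAP 4.5). The documents do not show that the change was prompted by the data.

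**What to change.** In SAP 6.3, add rows with n, mean, SD, minimum and maximum for distal-level change in subjects with OLE-baseline entry scores 2 and 3, and for mid-level change in entry scores 4 and 5. Label these as the protocol-defined endpoints. Keep the all-subject rows and label them supplementary. Reword the third bullet of SAP 8 to say that the subgroups are reported descriptively, with no p-values or inference because of small n. SAP 2.2.4 can then stay as written, and the three sections agree.

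The cost is SAP wording and a few rows in tables already planned, using a variable that SAP 5.3 already requires. The downside is that the subgroup summaries will be imprecise and may rest on very few subjects, so n must be shown in each row.
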